8.6 SAFETY OVERSIGHT

Safety oversight will be under the direction of a DSMB composed of individuals with the appropriate expertise, including [name], [name], and [name]. The DSMB will meet at least semiannually to assess safety and efficacy data on each arm of the study. The DMSB will operate under the rules of an approved charter that will be written and reviewed at the organizational meeting of the DSMB. At this time, each data element that the DSMB needs to assess will be clearly defined. The DSMB will provide its input to the PI and study staff.

10 STATISTICAL CONSIDERATIONS

10.1 STATISTICAL AND ANALYTICAL PLANS

All statistical analyses will be performed in conjunction with the consultant biostatistician([name]). The proposed sample size of 20 subjects for the Phase II expansion cohort was determined to detect, with an 80% power at a 5% type-1 error rate, a change of 15.9 points on the primary endpoint (ie. SNOT-22 score) between baseline and 4 weeks. This calculation was based on two assumptions. The first is a target effect size of 15.9 which represents a conservative value derived from the established MCID for the SNOT-22 of 8.9[65] and the LSM change in SNOT-22 of 27.7 derived from our previous trial of oral Verapamil(Section R.4.d)[19]. The second is an anticipated standard deviation of 24 which is calculated from the standard deviations of 30 both at the baseline and 8 week time point observed in our oral Verapamil trial and an r2 of 50% between the two time points. With a significance level of 0.05, a standard deviation of 24, and 80% power, a sample size of 20 would be needed to detect a difference of 15.9. Analysis of efficacy will be based on an intention-to-treat population that will include all enrolled patients. A mixed-effect model with repeated measures approach will be used to independently analyze the change in the SNOT-22, VAS, and LKS. An intraclass correlation coefficient (ICC) will be calculated to assess inter-rater agreement with respect to the LKS scores. Descriptive statistics will be used for demographics, baseline characteristics, and safety variables. Linear regression models will be fitted to examine the interaction effect between baseline characteristics, whole mucus and exosomal P-gp concentrations, mucus and irrigant cytokine concentrations, and treatment on change in SNOT-22 while adjusting for the baseline SNOT-22 score. Statistical analyses will be performed using the statistical software SAS (SAS Institute Inc., Cary, NC)

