3 OBJECTIVES AND PURPOSE

Primary Objectives:

- Perform a Phase IB trial of topical intranasal Verapamil HCl BID to determine the Maximal Tolerated Dose(MTD) using an accelerated titration design with intra-patient dose escalation.
- Perform a Phase II trial of topical intranasal Verapamil HCl BID based on the MTD to determine safety and efficacy using both subjective and objective outcome measures of CRS.

Secondary Objective:

- Determine whether mucus derived exosomal P-gp can be used as a non-invasive biomarker of CRS by correlating it with baseline symptoms of CRSwNP and treatment response to topical Verapamil HCl at the MTD.

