The Phase II study will be an open label safety and efficacy expansion cohort using the MTD determined in the Phase IB arm. A total of 20 patients will be administered the MTD of topical Verapamil HCl in a 240mL buffered normal nasal rinse for 4 weeks BID. This sample size was calculated based on a power analysis derived from the results of our oral Verapamil trial. The first dose will be administered in in a 10th or 11th floor MEE clinic withhemodynamic monitoring. A medically trained member of the study staff with monitor the patient for one hour. Patients will be instructed on the how to properly perform the irrigation using a pre-recorded video demonstration. If no first-course DLT occurs then patients will continue taking the topical Verapamil dose BID. Patients will then return for follow-up visits at 1 week and 4 weeks. Subjective and objective outcome measures will be collected at each visit.

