6.1.7 STARTING DOSE AND DOSE ESCALATION SCHEDULE

Phase Ib Verapamil HCl dose will start at a total residual dose of 0.3mg. Dose escalations will be as follows: 0.3mg, 0.6mg, 1.2mg, 2.4mg, 3.0mg, 3.6mg. Participants will remain on a dose for at least one week before escalating.

Phase II dose will be determined by Phase Ib.

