6.1.8 DOSE ADJUSTMENTS/MODIFICATIONS/DELAYS

The Phase Ib dose will only be escalated if a participant has not experienced a DLT or 2 ITs on the previous dose. The Phase II dose will not be changed at any point during the 4 week course.

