10.6 MEASURES TO MINIMIZE BIAS

10.6.1 ENROLLMENT/ RANDOMIZATION/ MASKING PROCEDURES

Participants will be enrolled in the MEEI Sinus Center. Eligible patients will be informed about the trial by their physician in the Sinus Center. If they express interest a member of the study staff will enroll them after passing through all inclusion and exclusion criteria. There will be no blinding or randomization in either phase of this trial.

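### The section 10.1 regression includes an interaction with treatment, which cannot be estimated when every Phase II participant receives the same treatment

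*Combined protocol and SAP*

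**What the plan says.** Section 10.1 sets out the only analysis in section 10 that uses the biomarkers: "Linear regression models will be fitted to examine the interaction effect between baseline characteristics", whole mucus and exosomal P-gp, mucus and irrigant cytokines, "and treatment on change in SNOT-22 while adjusting for the baseline SNOT-22 score".

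The design sections leave treatment no room to vary in Phase II:

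- Section 4.1: "A total of 20 patients will be administered the MTD of topical Verapamil HCl".
- Section 6.1.8: "The Phase II dose will not be changed at any point during the 4 week course".
- Section 10.6.1: "There will be no blinding or randomization in either phase of this trial".

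The secondary objective in section 3 reads: "Determine whether mucus derived exosomal P-gp can be used as a non-invasive biomarker of CRS by correlating it with baseline symptoms of CRSwNP". It goes on to name response to topical verapamil at the MTD as the second thing to correlate with P-gp.

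Nothing else in section 10 covers this objective. The hypotheses in 10.2 concern SNOT-22, VAS and LKS only. Section 10.4.3 applies the primary-endpoint methods to the secondary endpoints, and section 4.2.2 does not list P-gp among those. Multiplicity (10.4.9) and exploratory analyses (10.4.11) are both marked not applicable.

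**The concern.** An interaction between a covariate and treatment is a comparison of covariate slopes between treatment groups. With a single group there is nothing to compare.

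Two things are at stake. First, the one model that serves the secondary objective does not fit the design. The analyst would have to choose a replacement, possibly after seeing the data, among two forms of P-gp and several cytokines, with no multiplicity rule.

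Second, the label could mislead. If the software drops the redundant terms, what remains is the slope of change on P-gp among treated patients. Reported under the heading of a treatment interaction, that slope would look like evidence that P-gp identifies patients who benefit from verapamil. Without a control group it could equally reflect prognosis, natural course or regression to the mean, since section 5.1 requires a baseline SNOT-22 of at least 30. Section 2.1 shows how readily such a relationship is read mechanistically: it takes the link between mucus P-gp and benefit in the earlier oral trial as a strong sign that verapamil acts through P-gp. That trial had a placebo group; this one does not.

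**Working it through.** **The plan's own figure.** The only sample size given is 20, for the primary endpoint. Inputs from 10.1 and 10.5: difference 15.9, SD 24, alpha 0.05 (sidedness not stated; two-sided assumed), power 80%. For a paired t-test the noncentrality is (15.9/24) × √20 = 2.96, which gives power 80.2%; n = 19 gives 78.0%. So 20 is reproduced. It says nothing about the biomarker regression, for which no size or power is stated.

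**Does treatment vary?** In Phase II there is one agent, one dose level, no dose change and no comparison group (4.1, 6.1.8, 10.6.1). Section 6.1.5 calls the Phase II dose the MAD and section 4.1 calls it the MTD. Those sections must be reconciled, but treatment is constant under either. Hence T = 1 for all 20 participants.

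**What that does to the model.** For one biomarker P and baseline SNOT-22 B, the model is

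change = a + g·B + b·P + c·T + d·(P×T).

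With T = 1 the T column equals the intercept column and the P×T column equals the P column:

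| Model | Columns | Rank |
|---|---|---|
| Intercept, B, P, T, P×T | 5 | 3 |
| Intercept, B, P | 3 | 3 |

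The shortfall of 5 − 3 = 2 is the treatment main effect and the interaction. Substituting T = 1 gives

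change = (a + c) + g·B + (b + d)·P.

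The data identify the sum b + d. They carry no information on how it divides into b (association without treatment) and d (modification of the treatment effect). More patients do not help.

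**What remains estimable.** Without the treatment terms the model has full rank, with 20 − 3 = 17 residual degrees of freedom if all 20 contribute. The slope on P is the adjusted association of P-gp with change among treated patients. The correlation of baseline P-gp with baseline symptoms needs no treatment contrast. Interactions between two covariates, such as P-gp with BMI, contain no T and are also estimable.

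**Precision at n = 20** (Fisher z, two-sided 0.05, one adjustment covariate):

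- Partial correlation detectable with 80% power: tanh[(1.960 + 0.842)/√(20 − 1 − 3)] = tanh(2.802/4) = tanh(0.700) = 0.60.
- Power at partial correlation r is Φ[4 × atanh(r) − 1.960]:

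| r | 4 × atanh(r) | Power |
|---|---|---|
| 0.3 | 1.238 | 24% |
| 0.4 | 1.695 | 40% |
| 0.5 | 2.197 | 59% |

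- If only 18 or 16 patients have usable samples (assumed, for range), the detectable value rises to 0.63 or 0.67.
- For the unadjusted correlation with baseline symptoms: tanh(2.802/√17) = 0.59.

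**The case against.** The strongest reply is that the objective never asked for an interaction. Section 3 asks for correlations, and the planned regression already has the right outcome, predictor and adjustment. Most software would drop the redundant terms and return the P-gp slope that is wanted. This stands, and it limits the point to the terms that contain treatment.

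A reader might infer that the biomarker objective has no valid analysis, or that the model cannot be run at all. The documents do not support either, because the reduced model has full rank and answers the response half of the objective. A reader might also infer that every interaction in the sentence fails. It can be read as covering interactions among the covariates, and those are estimable.

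Another reply is that treatment could mean dose, which does vary in Phase Ib: "Dose escalations will be as follows: 0.3mg, 0.6mg, 1.2mg, 2.4mg, 3.0mg, 3.6mg". Section 10.1 also speaks of an intention-to-treat population of all enrolled patients. But section 10.3 assigns Phase Ib to the safety dataset and the intention-to-treat dataset to Phase II, no pooling of phases is described, and the objective is set at the MTD. Within a Phase Ib patient, dose also rises with week, so dose and time would be confounded. Nor can treatment mean before versus after, because the outcome is already a change score.

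Finally, P-gp is not a listed endpoint, and the sample size and the SNOT-22, VAS and LKS comparisons are untouched. That is true, and it bears on weight rather than on correctness.

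**Conclusion.** The point holds for the treatment terms. In the single-arm, fixed-dose Phase II cohort, the treatment main effect and every interaction containing treatment have zero degrees of freedom. This rests on the regression being fitted to Phase II alone, as sections 3 and 10.3 indicate, and does not depend on any assumed effect size.

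The biomarker objective remains answerable as a pair of correlations. Two limits remain: section 10 has no written method for the correlation with baseline symptoms, and a single arm cannot separate a marker of drug benefit from a prognostic one. No section commits the sponsor to a predictive claim against control, so the misreading is a risk created by the wording, not something the plan asserts. The weight is moderate: the only secondary objective is affected and the primary analysis is not.

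**What to change.** Amend section 10.1, and enter the exploratory part under 10.4.11:

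1. Delete treatment, and every interaction containing it, from the regression.
2. Prespecify one main biomarker model: change in SNOT-22 from baseline to week 4 on baseline exosomal P-gp, adjusted for baseline SNOT-22, reporting the slope and 95% confidence interval. Name the baseline sample explicitly, since the schedule of events collects mucus at both baseline and day 28.
3. List whole mucus P-gp, the cytokines and any covariate-by-covariate interactions as exploratory.
4. Add the correlation of baseline exosomal P-gp with baseline symptoms, naming the symptom score and the coefficient, with its 95% confidence interval.
5. State that these results are associations in treated patients and do not show that P-gp modifies the effect of verapamil.

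This needs no new patients, visits or samples. The cost is a narrower biomarker claim, and the text should acknowledge that a partial correlation of 0.4 would be detected only about 40% of the time at n = 20.

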Exosomal P-gp, Whole Mucus, and Irrigant Th2 Cytokine Quantification: Whole mucus and exosomal P-gp will be quantified using a commercially available ELISA(USCN Life Sciences Inc., Wuhan, P.R. China) kit as previously described. Western blot will be used to confirm the ELISA findings. Briefly, 10 µg of total protein and Laemmli loading buffer (2x Laemmli sample buffer, Bio-Rad, Hercules, CA, with β-mercaptoethanol, Sigma, St. Louis, MO) will be denatured at 95°C for 3 minutes and separated on precast Novex® 4-20% Tris-Glycine Mini Protein Gels (1.0 mm, 9 wells, Life Technologies). Protein will be transferred onto a polyvinylidene fluoride membrane by iBlot® Dry Blotting System (Invitrogen, Carlsbad, CA). The membrane will be blocked and the primary antibody (Monoclonal Anti-P-glycoprotein Clone F4, 1:1000, in 5% milk in TBST) will be added and incubated at 4°C overnight. After 3 washes of 15 minutes each with TBST, the secondary antibody (Anti-Mouse IgG (Fab specific)-Peroxidase antibody produced in goat in 5% milk in TBST, Sigma) will be incubated for 1 hour at room temperature. The membrane will be washed again 3 times at 15 minutes each with TBST and SuperSignal™ West Pico Chemiluminescent Substrate (Life Technologies) will be applied for 5 minutes before visualization with ChemiDoc MP(Bio-Rad). Recombinant Pgp (USCN Life Sciences Inc., Wuhan, P.R. China) will be used as a control and a monoclonal anti-GAPDH antibody produced in mouse (Sigma Aldrich) will be used as a loading control. Pre and post-treatment Th2 associated cytokines in whole mucus and irrigant efflux including Eotaxin-3, Eosinophilic Cationic Protein(ECP), IL-6, IL-5, and TSLP which have been previously associated with successful CRSwNP treatment response[36][30][3][45] will be tested by commercially available ELISA.

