10.4.9 MULTIPLE COMPARISON/MULTIPLICITY

N/a

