10.5 SAMPLE SIZE

The sample size for the Phase II arm was determined in consultation with [name] (biostatistician). It is based on the MCID for the SNOT-22 and the least suare means value for the SNOT-22 that was determined by the previous oral verapamil trial conducted by [name]. The new, combined MCID for the SNOT-22 was determined to be 15.9. The standard deviation for this trial is 24. This was calculated using the standard deviation of the oral verapamil trial (30) and an r^2 of 50%. With a significance level of 0.05, a standard deviation of 24, and 80% power, a sample size of 20 is needed to detect a difference of 15.9.

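### Section 10.1 plans regressions of SNOT-22 change on at least 12 biomarkers in 20 single-arm participants: the treatment interaction cannot be estimated, false findings are uncontrolled, and exosomal P-gp has no named test

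*Combined protocol and SAP*

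**What the plan says.** All places are in the combined protocol and SAP.

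- Section 10.1 plans linear regressions for an interaction effect. The terms named are "whole mucus and exosomal P-gp concentrations, mucus and irrigant cytokine concentrations, and treatment on change in SNOT-22". Baseline characteristics are listed ahead of these, and the models adjust for the baseline score. It does not say whether the markers enter together or one at a time, which sampling time is used, which baseline characteristics are meant, or what significance level applies.
- Section 7.2.2: P-gp is measured in whole mucus and in exosomes. The cytokines, measured in whole mucus and in irrigant, include "Eotaxin-3, Eosinophilic Cationic Protein(ECP), IL-6, IL-5, and TSLP". The list is open-ended, so five is a minimum.
- Section 3: the only secondary objective is "Determine whether mucus derived exosomal P-gp can be used as a non-invasive biomarker of CRS". It is to be met by correlating exosomal P-gp with baseline symptoms and with treatment response.
- Section 10.2 has hypotheses for SNOT-22, VAS and LKS, and none for P-gp. Section 4.2.2 does not list P-gp among the Phase II secondary endpoints.
- Section 10.4.9, "MULTIPLE COMPARISON/MULTIPLICITY", and section 10.4.11 on exploratory analyses both read N/a.
- Phase II has 20 participants, all on the same agent (4.1), with a dose that stays unchanged for the four weeks (6.1.8) and no randomization (10.6.1).

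**The concern.** The biomarker question is a stated objective, yet the only analysis that bears on it is one sentence mixing a dozen or more markers, an open set of baseline characteristics and a treatment term. An interaction with treatment needs participants who differ in treatment, and here none do.

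Without that term, two readings remain. Fitted together, the markers nearly exhaust 20 observations and the exosomal P-gp coefficient becomes unstable. Fitted separately, exosomal P-gp is one of at least 12 tests with no error control, and a chance association with any of them could be reported as the biomarker result. Section 2.1 shows that such results carry weight: two regression associations from the oral trial, each with p = 0.01, are used there to argue for mechanism and for higher dosing.

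**Working it through.** **Inputs.** n = 20 (10.1, 10.5). P-gp measures: 2 (7.2.2). Cytokines: at least 5 in each of 2 fluids (7.2.2). One adjustment covariate, baseline SNOT-22 (10.1). The level of 0.05 is stated only for the SNOT-22 sample size (10.1, 10.5), so applying it to these regressions is an assumption.

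**The plan's own figure.** Section 10.5 states: "With a significance level of 0.05, a standard deviation of 24, and 80% power, a sample size of 20 is needed to detect a difference". The target there is 15.9 points. A two-sided paired t-test at 0.05 with a mean change of 15.9 and SD 24 has power 0.802 at n = 20 and 0.780 at n = 19. So 20 reproduces, but for the primary endpoint only. Nothing in the documents sizes the biomarker analysis.

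**Treatment interaction.** With every participant treated alike, the treatment variable is constant. Its column equals the intercept, and its product with a marker equals the marker's own column. The main effect and the interaction cannot be separated at any sample size.

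**Marker count.** 2 + 5 × 2 = 12, as a minimum.

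**Joint main-effects model.**
- Parameters: 1 intercept + 1 baseline SNOT-22 + 12 markers = 14.
- Residual degrees of freedom: 20 − 14 = 6, before any baseline characteristic. Three characteristics (an illustrative number) would leave 3.
- Expected R² if none of the 13 predictors is related to the outcome: 13/19 = 0.68. The fit would look strong with nothing there.

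**Separate models, each at an assumed 5%.**
- If the 12 tests are independent: 1 − 0.95^12 = 0.460.
- Independence is unlikely. Section 2.1 reports that IL-5 and TSLP secretion correlated with P-gp expression in explants, and the same cytokines are measured in two fluids from the same nose.
- Simulation of 20 participants and 12 null markers with equal pairwise correlation, each model adjusted for baseline SNOT-22 (8,000 runs per value; a repeat with 200,000 runs gave the same rounded results):

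| Assumed correlation | Chance of at least one false finding |
|---|---|
| 0.3 | 40% |
| 0.5 | 33% |
| 0.7 | 24% |
| 0.9 | 14% |

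The documents give no correlation among the trial's own mucus and irrigant markers, so these values are a range and not an estimate.

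**Single-marker model.** Intercept + baseline SNOT-22 + exosomal P-gp = 3 parameters; 20 − 3 = 17 residual degrees of freedom.

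**The case against.** The strongest defence is that this is hypothesis-generating work in a small early-phase cohort. P-gp is not a listed endpoint and has no formal hypothesis, so nobody has said that a marker will be claimed at 5%. Section 3 also singles out exosomal P-gp and names correlation as the method. Both points stand as descriptions, and they limit the concern: a confirmatory marker claim is something a reader might infer, not something the plan states. They do not remove it. The question is a formal objective, the exploratory section is N/a, and section 10 never turns the objective into a named analysis. No correlation with baseline symptoms appears there at all.

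Three stronger readings are tempting, and the documents do not support them.

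- A reader might take 46% as the error rate of the plan. It is the value for 12 independent tests at 5% each. Independence is implausible here, and the plan sets no level for these tests.
- A reader might double the count because samples are taken before and after treatment, giving 1 − 0.95^24 = 71%. Section 7.2.2 states pre and post sampling for the cytokines only, and two values from one person are unlikely to be independent.
- A reader might infer an interaction model with more terms than participants. Section 10.1 speaks of models in the plural and does not clearly ask for marker-by-characteristic interactions. What is documented is that the form of the model is left open.

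**Conclusion.** The point holds, in three parts of differing firmness.

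- **Firm, with no numerical assumption:** the treatment interaction cannot be estimated in a single-arm, fixed-dose cohort, and section 10 contains no designated analysis of the only secondary objective.
- **Firm, by counting:** a joint main-effects model has at least 14 parameters for 20 people and at most 6 residual degrees of freedom, so its coefficients would not be reliable.
- **Conditional:** separate models at an assumed 5% carry up to about a 46% chance of at least one false finding if independent, and roughly 24-40% at assumed correlations of 0.3-0.7. That is about five to eight times the nominal 5%. Very high correlation (0.9) would bring it to 14%; testing baseline characteristics as well would raise it.

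The test of SNOT-22 change from baseline to week 4 is not affected.

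**What to change.** 1. In 10.1, delete the interaction with treatment.
2. Name as the main test of the secondary objective a regression of week-4 change in SNOT-22 on baseline SNOT-22 and baseline exosomal P-gp (17 residual degrees of freedom).
3. Follow it with a rank correlation of baseline exosomal P-gp with baseline SNOT-22, which covers the baseline-symptom half of the objective. State that SNOT-22 is the symptom measure chosen. Test the two in that fixed order, or split alpha between them: two independent tests at an unadjusted 5% would carry 1 − 0.95² = 9.75%.
4. Fit the other markers and the baseline characteristics one at a time, state the sampling time for each, label them exploratory, and report estimates with intervals and no unadjusted significance claims. A false-discovery adjustment is optional.
5. Amend 10.4.9 and 10.4.11, which now read N/a, to match.

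The cost is SAP wording only; the data are already to be collected. The price is that the remaining markers can no longer be claimed at an unadjusted 5%.
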